10.3.4.8 Plasma Glucose from YSI – Part A only

Hourly plasma glucose results obtained from YSI will be listed.

10.3.4.9 Blood Ketones from Finger-Stick

Details of the blood ketones assessments which were captured in the eCRFs will be listed.

10.3.5 Exploratory Statistical Methodology

10.3.5.1 Body Weight

The body weight will be summarized separately for Parts A and B by treatment group and timepoint, along with changes from baseline and percentage change from baseline. Figures of mean body weight, its changes and percentage changes from baseline will be presented

separately for Parts A and B by treatment. The baseline assessment for Part A subjects is defined as the measurement taken at the Lead-In (OBV) period for those subjects enrolled prior to Amendment # 1 of the protocol or the baseline visit for those thereafter. For subjects enrolled in Part B the baseline assessment is defined as the last assessment taken prior to Day 1 dosing.

10.3.5.2 QOL Questionnaires

The results from the WHO-5 Well-Being Index and T1-DDS QOL Questionnaires will be summarized separately for Parts A and B by treatment group as frequency tables and listed.

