Readings will be made by gently inserting the test strip into the meter, after which the subject will apply a small drop of blood from the finger to the white target area at the end of the test strip. The blood is then drawn into the test strip, at which time the blood ketone value will be displayed on the blood ketone test meter. Additionally, serum ketones and free

fatty acids will be measured during each weekly visit during the treatment period, as outlined in the Schedule of Assessments ([Appendix A](#)).

Quality of Life (QOL) Questionnaire

The Type 1 – Diabetes Distress Scale (T1-DDS) and WHO-5 Well-Being Index scales ([Appendix D](#)) will be provided to the subject at the beginning of the following study visits: Overnight Baseline Visit and Days 85 and 161(EOS) visits.

The T1-DDS is a validated survey instrument that assesses diabetes-related emotional distress and includes 28 items. Thinking back over the past month, the subject will be asked to indicate the degree to which each of the items may have been a problem.

The WHO-5 Well-Being Index scale includes five statements in which the subject will need to rate based on how the subject has been feeling over the last two weeks.

Blood Volume

It is anticipated that subjects enrolled in this study will agree to provide whole blood for safety, PK, and PD assessments during their participation in this study as listed in [Table 7-1](#):

Table 7-1: Total Blood Volume for samples collected prior to Protocol Amendment #1, for subjects participating in Part A

Procedure	Volume per Collection (mL)	Number of Collections	Total Volume (mL)
Safety (chemistry + hematology)	5	9	45
Fasting Plasma Glucose	2	15	30
Fasting Lipid Panel	5	9	45
Serum PK sample collection	4	6	24
Serum FSH levels (women only) ^Φ	5	1	5 ^Φ
HbA1c	6	4	24
Plasma Glucose via YSI	0.75	27	20
MMTT (glucose & insulin)	40	3	120
GLP-1 (active & total), Glucagon, Plasma insulin and C-peptide	4	6	24
Anti-REMD-477 Ab sample collection *	10 (first) / 5	3	20
Exploratory biomarker collection	30	3	90
Serum Ketones & free fatty acids	1.5	15	22.5
TOTAL **			464.5 469.5^Φ

* First collection is 10 mL, subsequent collections are 5 mL.

** Volume to be collected over approximately 238 days.

**Table 7-2: Total Blood Volume for samples collected under Protocol Amendment #1,
 for subjects participating in Part A**

Procedure	Volume per Collection (mL)	Number of Collections	Total Volume (mL)
Safety (chemistry + hematology)	5	9	45

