10. STATISTICAL CONSIDERATION

Study Endpoints, Subsets, and Covariates

Primary Endpoints:

- Change from baseline at Week 12 in daily insulin use.

Secondary Endpoints:

- Change from baseline at Week 13 in fasting glucose and glucose AUC after the MMTT – for Part A only.
- Change from baseline at Week 12 in average daily 24-h blood glucose concentration and time within target range as assessed by CGM and seven-point glucose profile.
- The product of the ratio of average glucose (Week 12/Baseline) and ratio of average insulin use (Week 12/Baseline).
- Subject incidence of adverse events and clinically relevant changes in medical history, physical examination, laboratory safety values, and ECGs.
- Incidence of hypoglycemic events.
- Change from baseline at Week 13 in HbA1c.
- Proportion of subjects who achieve HbA1c reduction of $\geq 0.4\%$.
- Change from baseline at Week 13 in fasting C-peptide and C-peptide AUC after MMTT and arginine challenge (for a subset of subjects who were enrolled prior to Protocol Amendment #1) – in Part A only.
- Change from baseline at Week 13 in peripheral levels of fasting glucagon, active and total glucagon-like peptide 1 (GLP-1), and glucagon and GLP-1 (active and total) AUC after MMTT challenge – in Part A only.
- REMD-477 plasma concentrations and incidence of anti-REMD-477 antibody formation.

Exploratory Endpoints:

- Change from baseline at Week 13 in body weight.
- Change from baseline in QOL score at week 13.
- Changes in intrahepatic lipid content as measured by MRI-PDFF (for a subset of subjects in Part B only)
- Changes in intrahepatic lipid content as measured by FibroScan® (for a subset of subjects in Part B only)

Sample Size Considerations:

The power calculation for the primary endpoint (difference in the change from baseline in daily insulin use) is based on the assumption that daily insulin requirement will not change in the placebo group and will decrease in the REMD-477 treatment group. Based on expected coefficient of variation of the daily insulin requirement of ~36%, it is estimated that ≥ 22 subjects in each group (treatment and placebo) will be sufficient to detect a difference of at least 30% with a power of 0.8, and an alpha value of 0.05. To ensure statistical power, and to avoid inadequacy due to unanticipated subject dropout, an N=25/group is used for each part of this study.

Access to Individual Subject Treatment Assignments

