Appendix D. Quality of Life Questionnaires

WHO-5 Well-Being Index

DIRECTIONS: Please indicate for each of the five statements which is closest to how you have been feeling over the last two weeks. Notice that higher numbers mean better well-being.

Example: If you have felt cheerful and in good spirits more than half of the time during the last two weeks, put a tick in the box with the number 3 in the upper right corner.

Over the last two weeks:	All of the time	Most of the time	More than half of the time	Less than half of the time	Some of the time	At no time
1. I have felt cheerful and in good spirits.	5	4	3	2	1	0
2. I have felt calm and relaxed.	5	4	3	2	1	0
3. I have felt active and vigorous.	5	4	3	2	1	0
4. I woke up feeling fresh and rested.	5	4	3	2	1	0
5. My daily life has been filled with things that interest me.	5	4	3	2	1	0

T1-DDS

Instructions

Living with type 1 diabetes can be tough. Listed below are a variety of distressing things that many people with type 1 diabetes experience. Thinking back over the past month, please indicate the degree to which each of the following may have been a problem for you by circling the appropriate number. For example, if you feel that a particular item was not a problem for you over the past month, you would circle "1". If it was very tough for you over the past month, you might circle "6".

		Not a problem	A slight problem	A moderate problem	A somewhat serious problem	A serious problem	A very serious problem
1	Feeling that I am not as skilled at managing diabetes as I should be.	1	2	3	4	5	6
2	Feeling that I don't eat as carefully as I probably should.	1	2	3	4	5	6
3	Feeling that I don't notice the warning signs of hypoglycemia as well as I used to.	1	2	3	4	5	6
4	Feeling that people treat me differently when they find out I have diabetes.	1	2	3	4	5	6
5	Feeling discouraged when I see high blood glucose numbers that I can't explain.	1	2	3	4	5	6
6	Feeling that my family and friends make a bigger deal out of diabetes than they should.	1	2	3	4	5	6
7	Feeling that I can't tell my diabetes doctor what is really on my mind.	1	2	3	4	5	6
8	Feeling that I am not taking as much insulin as I should.	1	2	3	4	5	6
9	Feeling that there is too much diabetes equipment and stuff I must always have with me.	1	2	3	4	5	6
10	Feeling like I have to hide my diabetes from other people.	1	2	3	4	5	6
11	Feeling that my friends and family worry more about hypoglycemia than I want them to.	1	2	3	4	5	6

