5.3 Exploratory Objectives

- To compare the effects of multiple doses of REMD-477 versus placebo on change from baseline at Week 13 in body weight.
- To compare the effects of multiple doses of REMD477 versus placebo on change from baseline at week 13 in Quality of Life (QOL) score.
- To explore the effects of multiple doses of REMD-477 on the intrahepatic lipid content as measured by magnetic resonance imaging – proton density fat fraction (MRI-PDFF) (for a subset of subjects in Part B only)
- To explore the effects of multiple doses of REMD-477 on the intrahepatic lipid content as measured by FibroScan® (for a subset of subjects in Part B only)

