10.3.3 Exploratory Endpoints

- Change from baseline at Day 85 (Week 13) in body weight.
- Change from baseline in QOL score at Day 84 (Week 13).
- Changes in intrahepatic lipid content as measured by MRI-PDFF (for a subset of subjects in Part B only)
- Changes in intrahepatic lipid content as measured by FibroScan® (for a subset of subjects in Part B only who underwent Fibroscan at baseline and post-treatment)

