10.3.4 Efficacy and Pharmacodynamic Statistical Methodology

10.3.4.1 General

All data, including derived parameters, will be listed and summarized for Part A and B separately. Absolute changes (and percentage changes, where applicable) from baseline will also be listed and summarized. Values outside the reference ranges will be flagged, if appropriate.

Preliminary analyses of variance will be performed to assess whether the baseline average daily insulin use and HbA1c levels among subjects are similar between the treatment groups. If any significant difference exists between any two treatments at the 5% level ($p \leq 0.05$), the variable will be used as a covariate in the repeated measures analysis of covariance (ANCOVA) as described in this section to adjust for any pre-intervention difference between treatment groups.

In all analyses, careful attention will be given to the appropriateness of the statistical procedure by determining whether necessary conditions are satisfied; e.g., normality and equal variance. When conditions are violated, the use of data transformations intended to produce data that satisfy normality and equal variance assumptions will be explored. If an appropriate transformation cannot be found, non-parametric methods may be used as an alternative to the more standard analyses.

For all repeated measures ANCOVA of efficacy and pharmacodynamic endpoints, the SAS codes used will be similar to the following:

```
proc mixed data=xxx;
class subject day treatment;
model variable = baseline subject treatment day treatment*day;
repeated day / subject=subject type=csh;
lsmeans treatment*day / pdiff cl alpha=0.05;
ods output lsmeans=lsm;
ods output diffs=diff;
run;
```

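### The quality-of-life endpoint is a change in score at Week 13, but the SAP defines no score and plans no change from baseline, only frequency tables and listings

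*SAP*

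**What the plan says.** The SAP's exploratory objective (5.3) is to compare REMD-477 with placebo on "change from baseline at week 13 in Quality of Life (QOL) score". Its endpoint list (10.3.3) has "Change from baseline in QOL score at Day 84 (Week 13"), and protocol section 10 has "Change from baseline in QOL score at week 13".

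Two questionnaires feed this endpoint. Protocol section 7 says that the T1-DDS "is a validated survey instrument that assesses diabetes-related emotional distress and includes 28 items", and that the WHO-5 "includes five statements in which the subject will need to rate". Appendix D prints both forms. WHO-5 items run from 0 to 5, with the note "Notice that higher numbers mean better well-being". T1-DDS items run from 1 (no problem) to 6 (a very serious problem).

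The QOL analysis is the single sentence of SAP 10.3.5.2: results are "summarized separately for Parts A and B by treatment group as frequency tables and listed". Protocol section 10 names no QOL method.

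**The concern.** The objective and endpoint call for a number per subject, its change from baseline, and a contrast between arms. The planned output is a count of responses by arm. Nothing in the plan turns the counted responses into the endpoint.

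The term QOL score is also open in three ways: which instrument supplies it, how items are combined, and which direction is favourable. The two instruments run in opposite directions, so even the sign of a benefit depends on the choice. If the choice is left until the data are in hand, a reader of the study report cannot tell whether the score was picked before or after the arms were seen.

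**Working it through.** The plan states no figure for this point, so the check sets the texts side by side.

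1. **What the endpoint needs:** a score per subject, a baseline, a Week 13 value, their difference, and a comparison with placebo (SAP 5.3 and 10.3.3; protocol sections 1 and 10).

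2. **Is a score defined?** No. Protocol section 7 and Appendix D give item counts and response options, but no total, mean, subscale or missing-item rule. SAP 10.3.5.2 adds none. SAP 10.1 says that missing values are not imputed, so a simple total is undefined for anyone who skips an item.

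3. **Is a baseline defined?** Only by default. SAP 10.1.1 takes the last value before first dosing unless stated otherwise, which would serve once a score exists. On timing, protocol section 7 names only the Overnight Baseline Visit for the questionnaires. That visit does not apply to Part A subjects enrolled at the time of Amendment 1, or to Part B.

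4. **Is a change from baseline planned?** Not for QOL. SAP 10.3.4.1 has the general sentence "Absolute changes (and percentage changes, where applicable) from baseline will also be listed and summarized", but it belongs to the efficacy and pharmacodynamic methods in 10.3.4. QOL is in 10.3.5, where body weight (10.3.5.1) has its own explicit wording on change from baseline and on timepoints. The QOL sentence has neither. Even if the general rule carried over, there is no QOL score for it to act on.

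5. **Is the departure declared?** No. SAP section 4 says that substantial differences from the protocol's statistical considerations will be identified. Section 12 lists the glucose-insulin product, the hypoglycemia definition and the LDL analysis, and is silent on QOL.

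6. **Which day is Week 13?** The Part A and Part B schedule footnotes in Appendix A and SAP 10.3.3 give Day 84. The protocol synopsis and section 7 give Day 85. The Part B schedule has no Day 84 visit, only Day 85 ± 2. Part A subjects who were ongoing or newly enrolled at Amendment 1 have all Week 13 procedures on Day 85.

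7. **Could a score be formed from Appendix D?** Arithmetically, yes. A WHO-5 sum runs from 5 × 0 = 0 to 5 × 5 = 25. A T1-DDS item mean runs from (28 × 1)/28 = 1 to (28 × 6)/28 = 6. Higher is better on the first and worse on the second. These are possible scores, not scores that the documents adopt.

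For scale, a two-sample t-test with 25 per arm, two-sided 5% and 80% power detects about 0.81 standard deviations (0.86 with 22 per arm). A defined score would give an estimate with an honest interval in each Part, not a confirmatory test.

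**The case against.** The strongest reply is that nothing is lost. Both questionnaires are collected and listed, and SAP section 4 allows additional analyses if the study report identifies them. A reader might infer from 10.3.5.2 that the comparison can never be made; the documents do not support that. What stands is that no score was prespecified, so a later one would be chosen with the data available. Unblinded preliminary analyses open to the sponsor's study team are permitted (protocol section 10, SAP section 11), and SAP section 12 refers to a first interim of Part A. The documents do not say that QOL was examined then, and no such inference should be drawn.

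A second reply is that the SAP treats its exploratory endpoints descriptively. Body weight gets summaries and figures without a model, and MRI-PDFF and FibroScan get summaries by treatment and timepoint. This is fair. The absence of a formal test for QOL is consistent with its neighbours and is not the defect. The defect is the missing score and the missing change.

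A reader might also infer that the tables will be item by item (5 + 28 = 33 items), too sparse to show an effect. The SAP does not specify that layout, and nothing in the documents shows that a shift in responses would go unseen. The table shells that SAP section 4 mentions are not among the documents reviewed. They might add detail, but 10.3.5.2 does not point to them for scoring.

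**Conclusion.** The concern holds in a limited form. The QOL endpoint is a change in score, and the planned outputs contain neither a score nor a change, so the SAP gives no value for its own endpoint. The data remain usable; what is missing is prespecification.

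The size is small. The endpoint is exploratory and lies outside the Hochberg procedure, which SAP 10.3.4.2 sets for daily insulin use. No primary, secondary or safety conclusion changes. The finding rests on the text of the two documents and assumes that no scoring rule sits in the unsupplied table shells. It does not depend on any sample-size or cell-count figure.

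**What to change.** Amend SAP 10.3.5.2 before database lock:

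- Define one score per instrument, with its direction and a rule for missing items. The WHO-5 sum (0–25) and T1-DDS item mean (1–6) are candidates, but they are an assumption to confirm against the instruments' scoring instructions.
- State the QOL baseline for each Part and enrolment group.
- Summarise Week 13 change from baseline by arm and Part, with the difference of each dose from placebo and a 95% CI, labelled exploratory. A baseline-adjusted ANCOVA is optional and would match the SAP's other models.
- Keep the planned frequency tables and state their timepoints.
- Reconcile Day 84 and Day 85 as the Week 13 QOL day across the protocol synopsis, section 7, Appendix A and SAP 10.3.3.

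If the sponsor wants item frequencies only, the alternative is to reword the objective and endpoint as descriptive and declare this in SAP section 12. That is cheaper but gives up the stated comparison.

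The main fix costs SAP wording, two derived variables and a few exploratory outputs, with no new data collection. The added intervals are exploratory contrasts without multiplicity control and should be reported as such.

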10.3.5.3 Intrahepatic lipid content measured by MRI-PDFF

For a subset of Part B subjects the intrahepatic lipid content measured by MRI-PDFF will be summarised by treatment and timpoint and listed.

10.3.5.4 Intrahepatic lipid content measured by FibroScan

For a subset of Part B subjects the intrahepatic lipid content measured by FibroScan will be summarised by treatment and timpoint and listed.

10.4 Safety and Tolerability Assessments

10.4.1 Adverse Events

A baseline sign and symptom is defined as an adverse event (AE) that starts after the subject has provided written informed consent and that resolves prior to the first dosing occasion, or an AE that starts prior to the first dosing occasion and does not increase in severity after dosing. A treatment-emergent AE (TEAE) is defined as an AE that occurs post-dose or that is present pre-dose and becomes more severe post-dose.

All AE listings and summaries will be presented separately for Parts A and B.

All AEs will be listed. The TEAEs will be summarized by treatment, severity, and relationship to the study drug. The frequency (the number of TEAEs, the number of subjects experiencing a TEAE, and the percentage of subjects experiencing a TEAE) of TEAEs will be summarized by treatment, and by Medical Dictionary for Regulatory Activities (MedDRA) system organ class and preferred term. The summary and frequency TEAE tables will be presented for all causalities and for those TEAEs considered related to the study drug (those that have a relationship of probably or possibly related). Any severe or serious AEs will be tabulated. For any AEs that change severity ratings the AE will be included only once under the maximum severity rating in the summaries.

Onset times post-dose will be calculated from the last dose administered.

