Study recruitment, progress and safety issues will be reviewed by the investigators, research nurse and research coordinators and communicated to the sponsor on a regular basis. The following will be reviewed: 1) subject enrollment, 2) preliminary findings that might affect the risk/benefit ratio or alter the procedures described in the protocol, 3) any clinically-significant out-of-range laboratory value and a course of action, and 4) any adverse or serious adverse events that might result from the research procedures.

The Safety Review Committee will review all available safety and PD data periodically during the study when approximately 33%, 66%, and 100% of the subjects in Part A have received a randomized treatment. After each safety data review, the Safety Review Committee will decide whether or not to continue with subject enrollment and dosing. Decisions to continue enrollment will be documented in the Safety Review Memo. REMD Biotherapeutics will issue a written notification of these decisions to investigators.

Determination of Adverse Event Severity and Relatedness

Adverse events will be coded per current MedDRA. Determination of the severity of adverse events will be consistent with Common Terminology Criteria for Adverse Events (CTCAE) V. 4.03. The relationship of an adverse event to treatment will be determined by the Investigator (see section 9: Reporting Procedures for All Adverse Events).

Dose Stopping Rules

Dosing will be stopped or modified if treatment-related AEs, changes in vital signs, ECG, or clinical laboratory results are observed and these changes pose a significant health risk, in the opinion of the Sponsor, Principal Investigator or Medical Monitor.

Medically significant AEs considered to be related to the investigational product and serious adverse events considered to be related to study procedures will be followed until resolved or considered stable.

A subject may be terminated at any point in time at the discretion of the Sponsor, Principal Investigator or Medical Monitor.

Stopping Rules for an Individual Subject:

At any time during the study, the subject must discontinue study drug treatment, if one of the following events occur:

- An increase of AST and/or ALT (> 3x ULN) are observed in the presence of increased (> 2x ULN) alkaline phosphatase and/or total bilirubin.
- A sustained AST or ALT increase, defined as three consecutive values of AST and/or ALT greater than 5x ULN within a period of 14 days.

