6 STUDY DESIGN

This is a randomized, placebo-controlled, double-blind study to evaluate the efficacy, safety, and PD of multiple doses of REMD-477 in subjects who have Type 1 diabetes and are currently receiving insulin treatment. This study will determine whether glucagon receptor blockade with REMD-477 can decrease daily insulin requirements and improve glycemic control after 12 weeks of treatment in subjects diagnosed with Type 1 diabetes with fasting C-peptide < 0.7 ng/mL at Screening.

The two part study (Parts A and B) will be conducted at multiple sites in the United States. In each part, approximately 75 subjects (150 subjects in total across Parts A and B) with Type 1 diabetes on stable doses of insulin will be randomized in a 1:1:1 fashion into one of three treatment groups (placebo, 35 mg REMD-477, or 70 mg REMD-477). The enrollment of Part B may be initiated prior to the completion of Part A. Subjects will receive once weekly SC injections of investigational product for 12 weeks and be followed for an additional 12 weeks during washout in the Safety Follow-up Period. At baseline, throughout the treatment period, and during the 12-week Safety Follow-up Period, subjects will be evaluated for measures of glycemic control, daily insulin requirements, and safety. For subjects enrolled in Parts A and B, CGM and seven-point glucose profile will be conducted to assess the effect of REMD-477 versus placebo on glucose variability and metabolic control. For a subset of subjects in Part A who were enrolled prior to Protocol Amendment #1, beta cell function after mixed meal and arginine challenge will be examined. For subjects in Part A, alpha cell function will be assessed by measuring fasting glucagon, active and total GLP-1, and glucagon and GLP-1 (active and total) AUC after the MMTT.

For a subset of subjects in Part A who were enrolled prior to Protocol Amendment #1, eligible subjects will be admitted to the clinical research unit (CRU) on the evening of the Overnight Baseline Visit (OBV) (which can occur between Study Day -8 to Day -2), the Week 13 Visit (admission Day 84), and the Week 24 Visit (admission Day 161). For ongoing subjects at the time of the Protocol Amendment #1, the overnight admissions to the CRU at Baseline, Week 13 and Week 24 will not occur.

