8 SAMPLE SIZE JUSTIFICATION

The power calculation for the primary endpoint (difference in the change from baseline in daily insulin use) is based on the assumption that daily insulin requirement will not change in the

placebo group and will decrease in the REMD-477 treatment groups. Based on an expected coefficient of variation of the daily insulin requirement of ~36%, it is estimated that ≥ 22 subjects in each group (treatment and placebo) will be sufficient to detect a difference of at least 30% with a power of 0.8, and an alpha value of 0.05. To ensure statistical power, and to avoid inadequacy due to unanticipated subject dropout, an N=25/group is used for each Part of this study.

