10 STATISTICAL METHODOLOGY

10.1 General

Data listings will be provided for the All Subjects Population. Summary statistics and statistical analyses will be performed for subjects included in the relevant analysis populations (Safety/PK/PD).

For continuous data, summary statistics will include the arithmetic mean, arithmetic standard deviation, median, minimum, maximum, and number. For log-normal data (eg, the Mixed Meal Tolerance Test [MMTT] parameters: areas under the concentration-time curve [AUCs]), the geometric mean and geometric coefficient of variation (CV%) will also be presented. For categorical data, frequency counts and percentages will be presented. Data listings will be provided for all subjects. For the calculation of summary statistics and statistical analysis, unrounded data will be used.

Outputs will be created separately for Parts A and B.

Missing values will not be imputed.

Data analysis will be performed using SAS® Version 9.4.

Analysis Data Model (ADaM) datasets will be prepared using Clinical Data Interchange Standards Consortium (CDISC) ADaM Version 2.1, and CDISC ADaM Implementation Guide Version 1.1. Pinnacle 21 Community Validator Version 2.2.0 will be utilized to ensure compliance with CDISC standards.

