10.4.2 Clinical Laboratory Parameters

Biochemistry and hematology data will be summarized separately for Parts A and B by treatment. Changes from baseline will be calculated.

Values for any biochemistry, hematology, and urinalysis values outside the clinical reference ranges will be flagged on the individual subject data listings.

AST, ALT, total and direct bilirubin will be summarized by treatment and timepoint. Changes from baseline will also be summarized.

The frequency of subjects who have a maximum ALT $>3x$ ULN for any post-dose timepoint will be presented by treatment group. Additionally, the frequency of subjects who have an ALT $> 3x$ ULN will also be presented for each assessment timepoint and treatment group. Similar tables shall also be presented for $>5x$ ULN and $>10x$ ULN. These frequency displays will also be provided for AST. The incidence of subjects who also have $>3x$ ULN increases in ALT and/or AST with $>2x$ ULN of total bilirubin will also be summarized by timepoint and treatment group.

A repeated measures ANCOVA will be used to compare the change from baseline in LDL cholesterol results between treatment groups on each day for Parts A and B separately. Dependent variables will be treatment, day, and the treatment by day interaction. The baseline variable will be used as a covariate.

Subject will be used as a random effect. The LS means for each treatment will be presented for each timepoint. Also, the difference from placebo, the 95% confidence interval of the difference from placebo, and p-value associated with the null-hypothesis of no difference will be for each day.

The SAS code will be similar to as shown below:

```
proc mixed data=xxx;
class subject day treatment;
model variable = baseline subject treatment day treatment*day;
repeated day / subject=subject type=csh;
lsmeans treatment*day / pdiff cl alpha=0.10;
ods output lsmeans=lsm;
ods output diffs=diff;
run;
```

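### Safety tables are split by Part (about 25 per arm) with no combined estimate, and the joint ALT/AST-plus-bilirubin criterion is planned by timepoint without a per-subject total

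*SAP*

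**What the plan says.** SAP 9 defines the analysis populations for each Part separately. SAP 10.1 adds: "Outputs will be created separately for Parts A and B". SAP 10.4.1 repeats this for adverse events ("All AE listings and summaries will be presented separately for Parts A and B"), and SAP 10.4.2 repeats it for biochemistry and hematology. No section names a safety output that combines the Parts. SAP 12, which lists changes from the protocol, does not mention the split. The protocol's Safety Analysis text describes all dosed subjects by treatment and does not refer to Parts.

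For the liver, SAP 10.4.2 plans three displays:

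- The number of subjects whose maximum ALT at any post-dose time exceeds 3x ULN, with the same for 5x and 10x, and all of it for AST.
- The same thresholds visit by visit.
- A joint criterion, ALT and/or AST above 3x ULN "with $>2x$ ULN of total bilirubin will also be summarized by timepoint and treatment group".

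The protocol's first individual stopping rule (section 6) is wider. It applies when AST and/or ALT elevations above 3x ULN "are observed in the presence of increased (> 2x ULN) alkaline phosphatase and/or total bilirubin".

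On size, SAP 8 says "an N=25/group is used for each Part of this study". SAP 6 gives about 75 subjects per Part and 150 overall, randomized 1:1:1 to the same three arms.

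**The concern.** Transaminase elevation is the risk that the sponsor's own earlier data point to. In the type 2 study the protocol reports ALT rises in 7 of 12 subjects of the 70 mg cohort, with one isolated reading of 18x ULN. It also expects substantial accumulation with weekly dosing. Part B adds liver biomarkers and liver imaging.

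Two features of the tables sit badly with that. First, the trial exposes about 50 subjects per arm, but every planned percentage uses half of them. Second, the joint transaminase-and-bilirubin criterion, the more specific indicator of liver injury, is planned only as a visit-by-visit display. A safety reader wants to know how many subjects met it at any time and how many had both elevations at different visits. The planned table answers neither question.

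**Working it through.** **The plan's own figure.** SAP 8 rests on an "expected coefficient of variation of the daily insulin requirement of ~36" per cent, a 30% difference, power 0.80 and alpha 0.05 (two-sided assumed; the SAP does not say). With n per group = 2(1.960 + 0.842)² × (0.36/0.30)² = 2 × 7.849 × 1.44 = 22.6, the result is 23, against at least 22 stated. That agrees closely. The SAP uses 25. Then 25 × 3 arms = 75 per Part, × 2 Parts = 150, so about 50 per arm. The documents give no precision figure for safety.

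**Are the Parts comparable for liver tests?** The two Schedules of Assessments give the same post-dose chemistry days: 8, 15, 29, 43, 57, 85 and 162 (end of study). Arms and the 12 weekly injections are also the same, with concurrent placebo in each Part.

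**Precision with no events.** The Clopper-Pearson upper limit is 1 − 0.025^(1/n):
- n = 25: 13.7%
- n = 50: 7.1%

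**Chance of seeing at least one case in an arm**, 1 − (1 − p)^n:
- p = 1%: 22% at 25, 40% at 50
- p = 2%: 40% at 25, 64% at 50
- p = 5%: 72% at 25, 92% at 50

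**Illustrative comparison.** No test on ALT or AST is planned. If a two-sided Fisher exact test at 0.05 were run, its power by full enumeration of both binomials would be as follows. All rates are assumed.

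| Placebo vs active | 25 per arm | 50 per arm |
|---|---|---|
| 2% vs 10% | 0.02 | 0.19 |
| 2% vs 15% | 0.12 | 0.51 |
| 2% vs 20% | 0.30 | 0.78 |
| 2% vs 25% | 0.52 | 0.93 |

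**The joint criterion by visit.** The gaps between successive post-dose chemistry days are 7, 14, 14, 14 and 28 days up to Day 85, then 77 days to Day 162. Suppose ALT exceeds 3x ULN at Day 57 and has fallen below it by Day 85, when bilirubin first exceeds 2x ULN. That subject meets the joint criterion at no visit and is absent from the table.

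The by-visit counts also cannot be turned into a number of subjects. Three cells of 1/25 in one arm could be one subject on three occasions (1/25 = 4%, exact 95% CI 0.1% to 20.4%) or three different subjects (3/25 = 12%, 2.5% to 31.2%).

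**The stopping rule beside the table.** The protocol rule counts alkaline phosphatase and/or total bilirubin above 2x ULN. The SAP table counts total bilirubin only.

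**The case against.** Much of the case on the other side stands.

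- **Per-subject liver tables exist.** A reader might infer that the liver signal is never estimated per subject. SAP 10.4.2 does not support that: maximum ALT and AST are counted per subject at three thresholds, within each Part.
- **Non-coincident peaks are not lost altogether.** If ALT is still above 3x when bilirubin rises, the subject is counted at that visit. If not, the subject is still in the maximum-ALT table, and out-of-range values are flagged in the listings. The omission is from the joint-criterion table only. Likewise, alkaline phosphatase is part of the chemistry panel, so it is summarized on its own.
- **Counts by Part can be added.** Each subject is in one Part and one arm, so 2/25 and 3/25 give 5/50 by hand. The split does not destroy information on maximum ALT, maximum AST or preferred terms. With no ALT test planned, the power figures only illustrate what 25 and 50 per arm can show.
- **The prior data do not give a rate above 3x ULN.** The 7 of 12 had rises up to 3x, in a cohort of 9 active and 3 placebo subjects. Only the 18x reading is documented above 3x: 1/12 = 8%, or 1/9 = 11% if that subject was on active drug. Near 10%, even the combined comparison has power of only 0.19.
- **The Parts differ in ways that matter for some events.** CGM is unblinded in Part A and blinded in Part B. The optional Day 1 insulin reduction appears only in the Part A text, and ketone finger-sticks are scheduled only in Part A. By-Part display is a defensible primary choice.
- **Table shells are in a separate document** (SAP 4) that is not among those reviewed. An any-time row could exist there.

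Addition by hand does not work for the joint criterion, because its counts are by visit. It also gives no Part-stratified difference from placebo for ALT, AST or adverse events.

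**Conclusion.** The point holds in a limited form. The SAP names no safety estimate that combines the roughly 50 subjects per arm. It plans the joint ALT/AST-and-bilirubin criterion without a per-subject total and without capturing elevations at different visits. It has no joint count for the alkaline phosphatase limb of the protocol's stopping rule; those two passages should be reconciled.

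The joint-criterion gap is the firmer half, because the planned output cannot be reworked to fill it. The combined-Part half concerns precision and presentation: a zero-event upper limit of 7.1% instead of 13.7%, assuming full planned enrollment and similar liver risk in both Parts. The power figures rest on assumed rates and an unplanned test. They do not show that the trial will miss a signal, and the 7 of 12 should not be read as support for the 15% to 25% rows. Nothing here affects the primary endpoint.

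**What to change.** Keep all by-Part tables and add, before database lock:

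1. Supplementary tables by arm with both Parts combined, for ALT and AST above 3x, 5x and 10x ULN (per-subject maximum) and for TEAEs. Give exact confidence intervals and risk differences from placebo stratified by Part. Keep hypoglycemia-related events by Part, or mark their combined figures for cautious reading, because CGM blinding and the Day 1 insulin reduction differ.
2. A per-subject table over all post-dose times of ALT and/or AST above 3x ULN with total bilirubin above 2x ULN, and separately with alkaline phosphatase above 2x ULN. Show whether the two elevations were at the same visit. State whether unscheduled draws count, since SAP 10.1.2 otherwise excludes them from summaries.

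Record both additions in SAP 12 and check the table shells for an existing any-time row. No new data are needed. The cost is a few extra descriptive tables and their programming.
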